Measures will be exclusively self-report questionnaires to minimize participant burden and have practical remote study procedures. Demographics including age, race/ethnicity, gender, income/work status, weight (for blood-alcohol-concentration calculation), verification of cell phone ownership and willingness to receive messages, certification of English fluency, and current residential zip code (to verify WA State residency) will be assessed at screening. Trauma exposure will be assessed at screening and at 3-month follow-up (intervening trauma exposure). We will use the Life Events Checklist (LEC; Weathers et al., 2013), a 16-item measure that queries on lifetime experience of commonly reported traumatic events (e.g., sexual assault, natural disasters) and identifies the most impactful, worst event in the person's lifetime.

Co-Primary Outcome Measures. Co-primary outcome measures will be given at screening or baseline and at all follow-ups. Power calculations were based on the heavy episodic drinking outcome (see power analysis section).

Drinking behavior will be assessed via well-validated measures that provide details on drinking patterns. Heavy episodic drinking over the past month (HED: 4/5 or more drinks per single occasion for women/men) will be assessed with the Quantity Frequency scale (QF; Baer, 1993) that asks about past month peak drinking occasion, how many drinks were consumed on that occasion, and over how many hours the drinks were consumed. Typical weekly alcohol consumption will be assessed using the Daily Drinking Questionnaire (DDQ; Collins et al., 1985); participants will report the number of drinks they typically consume each day. Negative

alcohol-related consequences will be assessed via the Short Index of Problems (SIP; Miller et al., 1995), which corresponds with longer measures of drinking consequences (Forcehimes et al., 2007).

PTSD symptom severity will be assessed using the PCL-5 (Weathers et al., 2013). The PCL-5 uses the event selected as the “worst” on the LEC to index PTSD symptoms to a target trauma. The PCL-5 is commonly used and has good test-retest reliability ($rs = .82\text{-.84}$) and strong convergent validity ($rs = .85\text{-.87}$) with other PTSD measures (Blevins et al., 2015).

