Once the participants complete the baseline assessment, they will be randomized using a web-based custom program. Participants are entered into the program by the project coordinator. Randomization will use stratified permuted block randomization in 8 strata with three stratified variables: PTSD severity (PCL-5 scores of 33-60 vs. ≥ 61), risk of alcohol use disorder (AUDIT scores < 20 vs. ≥ 20), and gender identity (male vs. any other gender identity). Within strata, conditions assignments are based on prior assignments to ensure balanced numbers across intervention conditions. Stratification aims to control representation of factors commonly related to intervention response across conditions.

Starting the Monday following randomization, intervention texts will be sent 3 days a week (Tuesday, Wednesday, Friday) for 4 consecutive weeks. Each participant will receive 2 texts, back-to-back, each day based on intervention condition (see below). The participant chooses what time of day they receive the texts.

A post-intervention assessment will be emailed the day after the last text has been received, and a follow-up survey will be sent 1-month and 3-months post intervention. Regular reminders will be sent to maximize completion of the follow-up surveys. All measures, procedures, and intervention delivery are done via automated text message or self-report computerized survey: study investigators and staff are not aware of individual participant intervention conditions.

Participants will be compensated for completing baseline and follow-up assessments. Compensation will be \$20 at baseline, \$25 at post, \$30 at 1-month, and \$35 at 3-month follow-up, given as Amazon gift cards. Gift card drawings after each of the follow-up assessments (five, \$50 Amazon gift cards) will be used to further encourage assessment completion. Participants will not be compensated for screening or for receiving messages.

Fraud Detection

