A priori decision rules will be applied to select the intervention condition that is most effective and the simplest to undergo further testing in a subsequent RCT. Consistent with best practices for studies aiming to select the most effective combination of intervention elements using a factorial design, we will use a process of elimination rather than hypothesis-testing approach in applying our decision rules (Collins, 2018). In this approach, a series of criteria will be applied, and intervention elements that fail to meet minimum criteria for efficacy will be ruled out until the strongest set of elements remains (Collins, 2018). Because Type I error is less of a concern in this approach than Type II error, significance will be defined as $p < .10$.

Decision rules are based on co-primary and secondary outcomes and do not include intervention completion rates. This decision reflects both the type of intervention (texts are passively delivered) and pilot findings (no participants withdrew from the pilot), thus non-completion rates are not expected to be a concern.

Decision rules will be as follows:

1. We will first examine main effects for PTSD and HED in a model without interaction terms. We will retain any enhancements for further consideration in Step 2 that have significant negative main effects for both outcomes. If none exist, we will retain enhancements with significant negative main effects on PTSD or HED alone.

2. We will then examine interaction effects (framing x growth mindset x time) for PTSD and HED among any enhancements with significant negative main effects. If there is one or more negative interaction terms, we will examine linear contrasts among the combinations of enhancements that are part of the interaction to determine whether adding specific enhancements leads to improvement. If this does not yield a clear conclusion in terms of the combination of effects to select, we will examine the direction and magnitude of the main and interaction effects for these conditions on secondary outcomes and participant satisfaction data. If there are no negative interaction terms, we will select any enhancements that had significant main effects and no evidence for negative impacts on outcomes.

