3. If there are no positive significant interactions or main effects for either PTSD or HED, we will repeat step 1 and 2 with other co-primary and secondary outcomes in the following order: alcohol use consequences (SIP), typical weekly alcohol consumption (DDQ), depression (DASS), and anxiety (DASS).
4. If effect sizes across conditions do not differ significantly from control (no framing, simple reminder), we will choose the control given that it is the simplest condition.

Power

The co-primary outcomes for this study are HED and PTSD symptom severity. Power calculations were conducted for HED, as its lower expected average values and non-normal distribution was expected to generate a more conservative estimate of sample size relative to PTSD symptom severity. Considering a base rate of 5.93 episodes of HED per week (based on our pilot data) and $\alpha = .05$, we determined that a sample size of $N = 500$ ($n = 75$ per condition; n

= 150 per comparison) would yield $>.80$ power to detect an 18% or greater difference in number of HED episodes between any two conditions (i.e., count ratio of 0.82).

Decision rules were revisited in response to reviewer feedback when submitting our protocol for potential publication. We realized that our original approach was not fully aligned with our power analysis or our overarching goal of identifying the most efficacious *and* simplest condition. We realized that a process-of-elimination approach starting with main effects was more in line with our goal (rather than first testing the hypothesis that the combination of growth mindsets and loss-framing would be the most efficacious condition). We thus altered our decision rules from what was originally submitted to the funder and will be testing main effects (rule 1) first, followed by interaction effects (rule 2). Further, given our process of elimination approach (vs. hypothesis testing), a *p*-value cut-off of 0.10 is appropriate (Collins, 2018). The power analysis was reviewed with these changes, and we anticipate having $>.80$ power to detect even smaller main effects (i.e., a count ratio of .89).

Assessing Differences by Condition

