We will use an intent-to-treat approach to analyze results and retain all available data. For each outcome, we will explore change over time by condition visually, using within-group pre-post effect sizes ($d = (M_{post} - M_{pre})/S_{dif}$), and in generalized linear mixed effects models. In mixed-effects models, we will test main effects for each enhancement (i.e., framing enhancements with no framing as the reference, growth mindset with no growth mindset as the reference) and time (baseline, post, 1-month, 3-month), and a 3-way interaction term for framing \times growth mindset \times time. We will evaluate the need for random effects for time, different specifications for time (e.g., linear, quadratic), and count regression forms of the mixed-effects model (e.g., Poisson, negative binomial, zero-inflated).

Missing Data

Mixed-effects modeling should yield unbiased estimates in the presence of missing data assuming data are missing at random—that is, missingness is only related to observed data, but not the unobserved data. We will explore missing data patterns according to baseline (time-fixed) values of variables and consider the inclusion of additional covariates that show strong associations with missingness above and beyond any other planned covariates. Should sensitivity analyses suggest that the findings may be dependent on unobserved data, we will consider the need for approaches to missing data (e.g., using the pattern-mixture approach to combine effects across missing data patterns to yield unbiased results).

References

Bedard-Gilligan, M. A., Dworkin, E. R., Kaysen, D., Ojalehto, H. J., Stappenbeck, C. A., & Lindgren, K. P. (2022). A pilot study on the feasibility, acceptability, and preliminary efficacy of a brief text message intervention for co-occurring alcohol misuse and PTSD symptoms in a community sample. *Journal of Anxiety Disorders*, 91, 102615.

Blevins, C. A., Weathers, F. W., Davis, M. T., Witte, T. K. & Domino, J. L. (2015). The posttraumatic stress disorder checklist for DSM-5 (PCL-5): Development and initial psychometric evaluation. *Journal of Traumatic Stress*, 28, 489–498. DOI: 10.1002/jts.22059

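### Rule 2 leaves the pre-randomisation baseline unadjusted, so comparisons between combinations are less precise than they need be, by an amount the documents do not fix

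*Combined protocol and SAP*

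**What the plan says.** Assessing Differences by Condition specifies generalized linear mixed models with main effects for framing, growth mindset and time. The levels of time and the interaction appear as "baseline, post, 1-month, 3-month), and a 3-way interaction term for framing", growth mindset and time. No two-way terms are listed. The form of time is left open (linear or quadratic are given as examples), as is the count distribution. The Missing Data section refers to planned covariates, but none is named.

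On timing, Procedures states: "Once the participants complete the baseline assessment, they will be randomized using a web-based custom program". Under Measures: "Co-primary outcome measures will be given at screening or baseline and at all follow-ups". So every co-primary outcome has a value from before allocation.

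Decision Rules, rule 2, tests the framing by mindset by time interaction. If a negative term appears, "we will examine linear contrasts among the combinations of enhancements that are part of the interaction". The rule does not say whether these are contrasts of change or of follow-up means, or at which visit. The same section ranks Type II error above Type I error, and for that reason "significance will be defined as $p < .10".

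**The concern.** Because allocation follows baseline, the six conditions have equal true baseline means by design. A model that still estimates baseline differences between conditions spends information on quantities known to be zero, and passes part of their sampling error into the condition-by-time contrasts. A random intercept does not recover this. If every cell has its own baseline mean, the contrast is still the unadjusted difference in change.

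Rule 2 helps choose the condition that goes forward to the next RCT. Its cell contrasts rest on about 75 participants per condition by the plan's figure, which makes them among the least precise comparisons in the trial. Under rule 4 the control is chosen when conditions do not differ significantly from it, so a missed effect changes the decision. The point concerns the Rule 2 models only. Step 1 uses a model without interaction terms and raises different questions.

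**Working it through.** **The plan's own power figure.** Power gives "Considering a base rate of 5.93 episodes of HED per week (based on our pilot data) and $\alpha = .05", a count ratio of 0.82 and "a sample size of $N = 500$ ($n = 75$ per condition". For a two-sample Poisson comparison, SE = sqrt(1/(75 x 5.93) + 1/(75 x 5.93 x 0.82)) = 0.0706, and z = -ln(0.82)/0.0706 = 2.809. Power at two-sided .05 is Phi(2.809 - 1.960) = .802. The stated >.80 reproduces as a single-occasion comparison of two cells, without baseline or repeated measures.

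**Assumptions for the check.** Gaussian outcome, equal variance at all visits, common correlation rho between visits, visits at about 0, 1, 2 and 4 months, two-sided p<.10. The documents give no rho for HED. For PCL-5 they give only a test-retest value of .82-.84, which measures reliability and not correlation across an intervention and follow-up. I therefore show rho = .5, .7 and .82.

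**Free baseline mean in every cell.** Let r be the variance with a common baseline divided by the variance with free baselines.
- Average of three follow-ups: r = [(1 + 2rho)/3 - rho^2] / [4(1 - rho)/3] = (1 + 3rho)/4.
- 3-month visit alone: r = (1 - rho^2) / [2(1 - rho)] = (1 + rho)/2.
- Linear slope: r = 8.75 / [21 - 49rho/(1 + 3rho)], where 21 and 7 (squared, 49) are the sums of squared times and of times, and 8.75 = 21 - 49/4.

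A contrast with 80% power under free baselines then has power Phi((1.645 + 0.842)/sqrt(r) - 1.645).

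| rho | Average: r, power | Slope: r, power | 3-month: r, power |
|---|---|---|---|
| .5 | .625, 93% | .781, 88% | .750, 89% |
| .7 | .775, 88% | .881, 84% | .850, 85% |
| .82 | .865, 85% | .932, 82% | .910, 83% |

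Below rho .5 the gain is larger: at .3, r for the 3-month visit is .65 and power 92.5%.

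**Only additive enhancement differences free at baseline.** This is the other reading of the listed terms, with the unlisted condition-by-time terms added so that the contrasts exist. A cell pair's baseline difference is then estimated from more than that pair. Its variance is a fraction f of the two-cell value: f = 1/3 for a mindset pair (averaged over three framings), 1/2 for a framing pair (averaged over two mindsets), 1/3 + 1/2 = 5/6 for cells differing in both, and 0 for the 2x2 interaction. The ratio becomes 1/[1 + f(1/r - 1)]. A six-cell generalized least squares calculation gives the same values.

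| Contrast | rho .5 | rho .82 |
|---|---|---|
| Mindset pair | 83-86% | 81-82% |
| Framing pair | 84-88% | 81-83% |
| Differing in both | 87-92% | 82-84% |
| 2x2 interaction | 80% (no gain) | 80% (no gain) |

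Ranges run over slope, 3-month visit and average.

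**Unequal variances.** With baseline SD s0 and follow-up SD s1, the single-visit excess of the change variance over the adjusted variance is (s0 - rho s1)^2. At rho .5 and s0/s1 = .8, r = .75/.84 = .893, and 80% rises to 84% (86% for the average). At s0/s1 = .7 it is 82% (83%). At rho .7 and s0/s1 = .7 the excess is zero and nothing is gained.

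**With the plan's inputs.** At 75 per cell, ratio 0.82, p<.10, rho .5 and one follow-up, the change contrast has the same variance as the single-occasion comparison, since 2(1 - .5) = 1. Its power is Phi(2.809 - 1.645) = .878, against Phi(2.809/sqrt(.75) - 1.645) = .945 adjusted. For a 2x2 interaction ratio of 0.82 the variance doubles, giving .634 against .742 under free cell baselines. These figures apply the linear-model ratio to a Poisson SE, so they are indicative only.

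**The case against.** The strongest reply is that no fixed loss can be shown. A reader might infer that the plan forfeits some 8 to 13 points of power. That range is the rho = .5 row of the free-cell table. It needs an assumed correlation, equal variances, a Gaussian model and a saturated baseline, and the documents establish none of these. Entry requires PCL-5 of 33 or more and heavy episodic drinking, which may shrink the baseline SD and the gain with it. HED will be analysed with a count model, for which nothing was computed. The plan lists no framing by mindset term, and under one coding of the listed terms the interaction loses nothing. All of this stands, and it limits the size of the point.

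It may also be said that stratification limits imbalance. It does so only in part: PCL-5 and AUDIT are each split once (at 61 and 20), differences within strata remain, and the strata are not listed as model terms. Nor does the stated interest in change over time argue for free baselines, because with equal true baseline means the constrained model targets the same differences.

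If rule 2's contrasts are of follow-up means instead of change, the coding question falls away, but unadjusted means are still less precise than adjusted ones (pair variance times n of 2.0 against 1.5 at rho .5).

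A reader might also infer bias, or a contradiction of the stated power. Neither follows. The estimand is sound, and the stated figure is a single-occasion calculation that a single-visit change contrast matches at rho .5 and exceeds above it.

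**Conclusion.** The point holds as an efficiency improvement of uncertain size, not as an error. The plan treats a pre-randomisation measurement as an outcome with free enhancement differences, and nowhere uses the knowledge that those differences are zero in truth. Under equal variances, comparisons between combinations lose precision on either reading of the model terms. For a contrast that starts at 80% power, the available gain runs from about 1 point (additive baseline, rho .82) to about 13 points (free cell baselines, rho .5). It is nil for the 2x2 interaction under the additive reading, and may vanish if the baseline SD is small enough relative to follow-up. These figures rest on the Gaussian, common-correlation approximation. Their extension to the count models is untested. In a plan that puts Type II error first, a gain of this kind is worth taking.

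**What to change.** In the Rule 2 models for PTSD and HED, and for SIP and DDQ if Step 3 is reached, adopt one of two specifications:

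- Keep baseline in the outcome vector, constrain its mean to be equal across the six conditions, and allow condition effects and their interaction only at post, 1 month and 3 months.
- Model the three follow-up visits with the baseline value of the same outcome as a covariate, for example log(baseline + 1) for counts. This is an alternative to the constraint, not an exact equivalent in a count model.

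List the two-way terms and the coding of time explicitly. Compute the Rule 2 linear contrasts from the chosen model at named follow-up time points. Settle this before outcomes are compared by condition.

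The cost is a sentence or two of plan text and one changed model statement. No new data or participants are needed, and the constraint is justified because randomisation follows baseline.

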Secondary Outcome Measures. Secondary measures will be given at baseline and 3-month follow-up. They include the Alcohol Use Disorders Identification Test (AUDIT; Babor et al., 2001), the Depression Anxiety Stress Scales (DASS-21; Lovibond & Lovibond, 1995), the Customary Drinking and Drug Use Record (CDDR; Brown et al., 1998), the Drug Abuse Screening Test (DAST-10; Skinner, 1982), and treatment services received. A study reactions questionnaire will be given at post-intervention and 3-month follow-up to assess satisfaction with the texts and study and skill use. This measure will be used for descriptive purposes to assess the intervention’s feasibility and acceptability.

Enhancement Measures. Measures assessing avoidant coping and mindsets will be included to allow for secondary analyses to test mechanisms of action for the enhancements (Framing: approach; Mindsets: growth mindset). The 7-item avoidant coping scale assesses the extent to which individuals endorse avoiding problems and challenges (Ottenbreit & Dobson, 2004). For mindsets, a 3-item scale based on work by Dweck (1999, 2006) will assess beliefs about the changeability of PTSD symptoms, AM, and coping strategies.

Moderator Measures. To assess whether severe psychopathology associated with PTSD+ AM is a predictor of intervention response, we will assess severe mental illness and suicidality at

baseline. We will include a 4-item history of bipolar disorder and schizophrenia screening measure (Unutzer et al., 2001) and the 2-item screening version of the Columbia Suicide Severity Rating Scale (C-SSRS; Posner et al., 2011).

Procedures

Participants will follow a link included in the study advertisements to an online screening survey. The survey will start with an information statement to obtain consent, followed by self-report questionnaires assessing inclusion criteria. Participants deemed eligible from screening will be scheduled for a 5-minute verification phone call to review study procedures, allow the participant the opportunity to ask questions, obtain verbal consent, and verify participant identity. Immediately after verification, we will send baseline assessment via email. Participants will have 7 days to complete it to be officially enrolled in the study.

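### Does naming only the three-way framing × mindset × time term, without its two-way terms, make the Rule 2 interaction test invalid?

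*Combined protocol and SAP*

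**What the plan says.** Assessing Differences by Condition says the mixed models will test a main effect for each enhancement ("framing enhancements with no framing as the reference, growth mindset with no growth mindset as the reference"), a main effect of time with baseline as one of four levels, "and a 3-way interaction term for framing", growth mindset and time. Random effects for time, the form of time and the count distribution are left open. The two-way terms are neither listed nor ruled out.

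Decision Rules, rule 1 works from main effects alone: "We will first examine main effects for PTSD and HED in a model without interaction terms". Rule 2 follows: "We will then examine interaction effects (framing x growth mindset x time) for PTSD and HED among any enhancements with significant negative main effects". If a negative term appears, "we will examine linear contrasts among the combinations of enhancements that are part of the interaction". If that is unclear, the plan turns to "the direction and magnitude of the main and interaction effects for these conditions on secondary outcomes" and to participant satisfaction. If there is no negative term, "we will select any enhancements that had significant main effects and no evidence for negative impacts on outcomes".

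**The concern.** Read as a complete model formula, the list has a gap. Randomization makes the groups alike at baseline, so an enhancement shows itself as a different change over time, which framing × time and mindset × time would carry. Without those terms, and with products of reference-coded indicators, the single-enhancement cells must follow the control time course apart from a constant shift. Their extra change then loads on the only remaining term that varies with both condition and time, the three-way term.

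That term would turn negative when mindset alone works, and could turn negative when two enhancements are redundant and the true interaction is positive. Rule 2 acts on its sign, and is reached only after Rule 1 has found an effect. At stake would be the choice between a combination and a simpler condition, which is the purpose of the trial.

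**Working it through.** **Inputs from the plan.** 75 per condition and a count ratio of 0.82 with base rate 5.93 (Power); four time points including baseline (Assessing Differences by Condition); p < .10 (Decision Rules; taken as two-sided).

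**Assumed.** A 0.3 SD benefit appearing as a step after baseline; within-person correlation ρ = .3/.5/.7 with compound symmetry; normal outcome, known variance, complete data. Triplets below follow that order of ρ.

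**1. The plan's own figure.** For 75 versus 75 at two-sided .05, SE = √[1/(75×5.93) + 1/(75×5.93×0.82)] = 0.0706. Then |ln 0.82|/SE = 0.1985/0.0706 = 2.81 and power = Φ(2.81 − 1.96) = .80, as stated. This confirms the cell size; the plan gives no power for the interaction.

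**2. Literal fit, only mindset works (true interaction 0).** Generalized least squares on the six cells and four times gives an expected loss × mindset × time coefficient of −.176/−.196/−.210, SE .106/.096/.078. P(significantly negative) = Φ(−1.645 − b/SE). At ρ = .5 this is Φ(−1.645 + 2.04) = .65; across ρ it is about .51/.65/.85.

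**3. Two-way terms included.** The expected coefficient is 0. The contrast uses four cells, each a mean of three follow-ups minus baseline, so SE = √[4(1−ρ)(1+1/3)/75] = .223/.189/.146. P(significantly negative) = .05, as it should be.

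**4. Redundant pair (true interaction +.30).** The literal fit gives −.032/−.076/−.111, significantly positive in 2.6/0.7/0.1% of trials. With two-way terms it gives +.300, significantly positive in 38/48/66%.

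So the distortion of the coefficient is real if the list is fitted literally.

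**5. Carried through the rules.** Rule 2 looks only at enhancements that passed Rule 1. In the mindset-only case, loss framing and mindset both pass in 4.9/4.5/4.3% of trials, so the 51/65/85% falls to 2.5/3.0/3.6% of trials that both pass and show a significantly negative term. The table gives the probability that the loss-plus-mindset pair is kept, requiring both to pass Rule 1 on one outcome and, where contrasts are triggered, the pair to beat each single enhancement (200,000 simulated trials per setting).

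| What Rule 2 acts on | Truth | Literal list | With two-way terms |
|---|---|---|---|
| Significantly negative term | redundant | .302/.219/.166 | .302/.219/.166 |
| | additive | .851/.727/.611 | .847/.721/.603 |
| | mindset only | .048/.045/.042 | .047/.044/.041 |
| Any negative sign | redundant | .243/.187/.154 | .277/.208/.163 |
| | additive | .850/.727/.611 | .777/.638/.517 |
| | mindset only | .045/.043/.042 | .035/.032/.030 |
| Significantly negative term triggers contrasts; significantly positive term counts as a negative impact | redundant | .294/.217/.166 | .187/.115/.056 |
| | additive | .851/.727/.611 | .804/.685/.573 |

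Under the first reading nothing of practical size changes. Under the second, the two-way terms make selection worse in two of the three truths: the additive pair is kept less often by .850−.777 = .073, .727−.638 = .089 and .611−.517 = .094, and the redundant pair is kept slightly more often. Only the third reading shows a clear gain for the redundant pair (.294−.187 = .107, .217−.115 = .102, .166−.056 = .110), at a cost of about .04 to .05 for the additive pair.

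**6. Software that expands factors.** If the three-way product of factors is expanded to all 24 cell means, contrasts between conditions are correct even from the literal list. The joint three-way test still mixes in two-way effects (17 df; rejects in 60/77/95% in the mindset-only case, against 10% on 6 df with two-way terms).

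**The case for a change.** The strongest reply is that a pre-specified model behind a decision rule should not rest on convention. The plan says which model features stay open, and the two-way terms are not among them. The effect is not confined to normal outcomes: in Poisson simulations at the plan's count ratio of 0.82, with one active enhancement and no synergy, the literal three-way test rejects in 68–70% of trials, against 7–12% with the two-way terms. Contrasts from the literal reference-coded fit are biased too. With linear time, ρ = .5 and a gain-framing effect of 0.30 SD alone, gain plus mindset minus gain alone has expectation −0.18 SD when the truth is 0. For the tie-breaker on secondary outcomes, measured only at baseline and 3 months, a redundant pair would show a negative sign in 72/81/90% of trials instead of 14/10/5%.

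The arithmetic stands, and so does the point that the wording is incomplete: a three-way estimate from a literal fit could not be read as synergy. What does not stand is the step from an unlisted term to an invalid test. The text says which effects will be tested; it does not set out a design matrix, and nothing forbids the usual lower-order terms. The tie-breaker applies only when contrasts are unclear, alongside main effects and satisfaction data, and no effect on selection has been shown for it. The one sizeable gain depends on treating less-than-additive benefit as "we will select any enhancements that had significant main effects and no evidence for negative impacts on outcomes" would treat harm. That is a separate ambiguity, and listing the two-way terms would leave it open.

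**Conclusion.** No change to the plan is needed. The two-way terms are unmentioned rather than excluded, and an analyst following ordinary practice would include them, after which the three-way test has its nominal error rate. If the list were nevertheless fitted literally, the coefficient would be badly distorted, but the selected condition would barely change when a significantly negative term triggers the contrasts: differences are at most .008 in the three truths examined. If any negative sign triggers them, the changes are mixed, and the largest is a loss of .07 to .09 in keeping a truly additive pair.

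The sizes rest on the assumed 0.3 SD step effect, the three correlations, complete data, known variance and a single outcome passing through Rule 1. With both outcomes modelled, the redundant pair is kept in .15 to .27 of trials under either fit when a significantly negative term is the trigger, with a largest gap of .03. That the two-way terms remove the distortion does not depend on these assumptions.
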